Based on the literature and our own experience we estimated an approximate occlusion rate of 20% with the standard treatment (saline + heparinized saline flush as described above). The power analysis conducted by [name] determined that, using a two-group normal approximation test of proportions with a one-sided .05 significance level, a sample size of 198 participants per group will have 80% power to reject the null hypothesis that the proposed method is not inferior (i.e. the difference in proportions between the proposed method and the standard method is greater than 0.10). Thus, we will continue data collection until 198 have been completed in each group for a total of 396 study participants who completed 6 months of data collection. To date (July 3, 2019), 69.7% of patients enrolled in the study are able to complete 6 months of data collection without withdrawing for an exclusion criterion (ex: transferring to hospice, being started on an anticoagulant, etc). Therefore, we plan to consent 575 patients to result in 396 who complete the study. Once 396 patients have completed 6 months of data collection will stop and any remaining active participants will be withdrawn from the study.

Data Collection:

Independent Variables: Method for flushing implanted port catheters:

• 20 mL of saline followed by 5 mL of Heparinized saline in a concentration of 100 units/mL

OR

• 20 mL of saline only

Dependent Variables:

Primary Outcomes

- Occurrence of first complete (can neither withdraw blood nor flush the catheter) occlusion
- Occurrence of first partial (able to flush but unable to withdraw blood) occlusion
- Frequency with which alteplase (CathFlo) has to be utilized to resolve an occlusion

Secondary Outcomes

- Number of subsequent occurrences of complete or partial occlusions after the first occurrence.
- Amount of time in days that a port remains patent (flushes easily and able to obtain a blood return).
 - Amount of time between entrance in study and first incidence of partial or complete occlusion
 - Amount of time between incidences of partial or complete occlusion.
- Occurrence of other complications:
 - Central Line-Associated Blood Stream Infection (CLABSI) a laboratory-confirmed (recognized pathogen cultured from one or more blood cultures; organism cultured from blood is not related to an infection at another site) blood stream infection that is considered central line associated (CDC, 2012).
 - Develops complication related to Heparin

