Participants in the control group will have their implanted port catheters flushed according to the established site's policy. Following the use of the port catheter with no continuous fluids running, or before de-accessing a port catheter (removing the port needle), the port will be flushed with 20 ml of normal saline and 5 ml of heparinized saline in the concentration of 100 units of heparin per ml.

Participants in the intervention group will have their ports flushed with normal saline only. That is, following the use of the port catheter with no continuous fluids running, or before de-accessing a port catheter (removing the port needle), the port will be flushed with 20 ml of normal saline. Turbulent flushing technique (the solution is injected using a push/pause technique every 1 mL) will be used in both groups and all accessed port catheters will have a neutral displacement connector. The MicroCLAVE[®] Clear displacement connector (ICU Medical, Inc., San Clemente, CA, USA) is the current product in use. Participants in both groups will be seen in a TriHealth Cancer Institute Infusion Center or the UCMC Barrett Infusion Center at a frequency consistent with their individual treatment plan and as outlined in the site's policy. Participants will remain in the study for 6 months or until they experience one of the potential risks noted below. Participants will be considered as having completed the study if they participate for 6 months.

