Statistical Analysis: Descriptive statistics will be used to describe the participants. Differences between groups on the dependent variables will be calculated using t-test, Chi-Square or Fisher's exact test as appropriate for the level of data under analysis (also see discussion regarding interim analysis). Regression analysis will be used to determine the effect of the moderating variables on the occurrence of occlusion in the implanted ports. Participants in the control group and intervention group will be further stratified based on frequency of port flushing. Differences in the rate of occlusion between stratified groups will also be calculated.

Ethical Considerations: The purpose of this study is to determine the safest and most effective flushing solution(s) for maintaining patency in implanted port catheters. In so doing, study participants could be placed at potential risk for catheter occlusion. All catheter occlusion will be treated according to the site's policy, i.e., the instillation of alteplase (CathFlo) (see Appendix A). Potential study participants will be made aware of

the risk when enrolled in the study (See Appendix B (V.2, 2-20-2015) script for recruiting patients into the study and Appendix F, the Informed Consent Statement).

- **Informed Consent:** Patients who meet inclusion criteria will be approached by a member of the research team who will explain the study, implications of their participation and review the Informed Consent Statement and HIPAA Authorization Form(s) (see Appendix F and G). Participants will receive a copy of the signed Informed Consent Statement and HIPAA Authorization. The original signed Informed Consent Statement and HIPAA will be stored in a locked cabinet at a TriHealth office or locked location at UCMC, or an off-site locked storage area, for six years after the study is closed at which time the documents will be destroyed via mechanical shredder.

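### Secondary outcomes in days fall by inference to a t-test, with no value or censoring rule for ports that never occlude or participants who leave early

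*Combined protocol and SAP*

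**What the plan says.** Under Dependent Variables, Secondary Outcomes, the protocol lists "Amount of time in days that a port remains patent", with two sub-items: "Amount of time between entrance in study and first incidence of partial or complete occlusion" and "Amount of time between incidences of partial or complete occlusion".

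Statistical Analysis covers every dependent variable in one sentence: "Differences between groups on the dependent variables will be calculated using t-test, Chi-Square or" Fisher's exact test, according to the level of data. The only model is for a different purpose: "Regression analysis will be used to determine the effect of the moderating variables on the occurrence of occlusion". No time-to-event method is named anywhere in the document.

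On follow-up, the sample-size text under Recruitment reports that "69.7% of patients enrolled in the study are able to complete 6 months of data collection", and that once 396 have completed, "any remaining active participants will be withdrawn from the study". Experimental Aspect of the Study says "Participants will remain in the study for 6 months or until they experience one of the potential risks noted below". The same section then ends participation after three consecutive occluded visits, after an occlusion that cannot be resolved and leads to port removal, after HIT or heparin allergy, and after a heparin flush in the saline arm. These rules say when data collection stops. They do not say how the days accrued up to then enter the analysis.

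**The concern.** Days are continuous, so of the three named tests only the t-test fits. The plan never makes that assignment itself. A t-test needs one number per participant, and most participants have no observed time to occlusion. The analyst would have to choose among at least four data sets:

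- **Occluders only.** This compares when ports failed and ignores how many failed.
- **All observed days.** This counts early leaving as short patency, so unequal drop-out biases it.
- **Completers only.** This avoids that bias if drop-out is independent of occlusion. But completion means six months of participation, and repeated or unresolved occlusion ends participation, so the worst ports can be left out. If participation really ended at any occlusion, as one sentence literally reads, no completer would have occluded.
- **Occluders plus completers.** This keeps observed failures but drops the event-free time of those who left.

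Unequal drop-out is plausible from the plan's own rules. The heparin-flush withdrawal applies only to the saline arm, and HIT or heparin allergy is expected mainly in the heparin arm. The wallet card limits the first route. The net direction is unknown.

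**Working it through.** **Inputs from the protocol.** Control occlusion rate 20%, margin 0.10, one-sided alpha 0.05, power 80%, 198 per group, 69.7% completing, 575 consented, six months' follow-up.

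**The plan's own figures.** n = (1.645 + 0.842)² × 2 × 0.20 × 0.80 / 0.10² = 197.9, so 198 per group, as stated. For drop-out, 396 / 0.697 = 568.2, so 569, close to the stated 575. Neither figure depends on the outcomes in days.

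**How many participants the gap touches.** 198 × 0.80 = 158 control ports never occlude. At 30%, 198 × 0.70 = 139. Early leavers: 100% − 69.7% = 30.3%, and 575 × 0.303 = 174 participants.

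**Why occluders only sees almost nothing here.** Assume exponential times over τ = 182 days, with λ = −ln(1 − p)/τ.

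- Mean day among occluders, 1/λ − τ(1 − p)/p: 87.6 at p = 0.20 and 85.6 at p = 0.30, a gap of 2.0 days.
- Mean days capped at τ, p/λ: 163.1 and 153.1, a gap of 10.0 days.

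**Simulation.** Exponential occlusion and drop-out times, independent of each other; administrative end at 182.5 days; two-sided 0.05; 10,000 trials per main scenario and 5,000 for the other hazard shapes and 21-day visits. These are tests of difference, as Statistical Analysis words them. With drop-out, n = 575/2, about 287 per arm.

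Power with equal 30.3% drop-out:

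| Analysis | 20% vs 30% | 10% vs 20% |
|---|---|---|
| t-test, occluders only | 5.8% | 5.3% |
| t-test, all observed days | 33.9% | 33.9% |
| t-test, completers only | 53.9% | 70.0% |
| t-test, occluders plus completers | 61.7% | 78.5% |
| Log-rank, all randomised | 72.8% | 87.1% |

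- With full follow-up and 198 per arm, at 20% vs 30%: t-test on days 53.1%, log-rank 63.2%.
- If an assumed 20% or 40% of occluders are terminated and so are not completers, completers-only power at 20% vs 30% falls to 47.0% or 39.6%.
- If occlusion is seen only at assumed 21-day visits, the 20% vs 30% column becomes 5.4%, 26.2%, 49.9%, 57.1% and 70.8%.

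Type I error, with no true difference:

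- No drop-out or equal drop-out: 4.7-5.2% for every analysis.
- Assumed 28% vs 32.6%: all observed days about 13%.
- Assumed 25% vs 35%: all observed days 42-43%. Saline appears 8.9 days shorter or 9.0 days longer, depending on which arm loses more.
- In these unequal cases: completers only 4.7-4.8%, occluders plus completers 5.3-7.2%, log-rank 5.2%.

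A true 20% vs 30% with drop-out of 35% heparin and 25% saline: all-observed-days power 5.3%, log-rank 72.4%. A real excess in the saline arm would be masked.

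**Hazard shape (full follow-up, 198 per arm, 20% vs 30%).** If all the excess falls in months 4-6: t-test on days 18.9%, log-rank 59.3%. If all of it falls in months 1-3, the order reverses: t-test 82.4%, log-rank 69.1%.

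**The case against.** The strongest reply accepts the omission and disputes its size.

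- **The worst figures belong to one reading.** The two time intervals are sub-items of days patent. If they define it, a port that never occludes simply has no value, and all observed days is not an outcome the plan states. Recruiting until 198 have completed per group points more towards completers only, whose type I error stays near 5%. This is fair. But the parent item alone permits all observed days, and no sentence defines the completers as the analysis set.
- **The drop-out splits are assumed.** No drop-out by arm is given. At a gap of 1.6 points (29.5% vs 31.1%) type I error for all observed days is only about 6%, and at 2.5 points about 7%. The HIT figure of 1-5% in the background concerns heparin exposure in general, so it is weak support for a ten-point gap. This stands: the 42-43% is conditional.
- **Log-rank is not always better.** It loses if the excess is early. Occluders-only power also depends on hazard shape, at about 32% (late excess) and 43% (early excess) with full follow-up. This stands too. It argues for fixing the method in advance, not for leaving it open.
- **Censoring may be informative.** Starting an anticoagulant or having a thrombotic event may relate to occlusion, and the simulations do not test that. This limits the proposed remedy. It limits a t-test among completers for the same reason.

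**Conclusion.** The concern holds. The document-based part is firm: the stated methods do not fit the outcomes in days, and no rule covers the roughly 80% of control ports expected not to occlude or the 30.3% of participants who do not complete. The choice left open moves power from 5.8% to 61.7% in one and the same scenario, and one permissible choice can inflate type I error to 42-43%.

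Those magnitudes are illustrations. They rest on assumptions that the documents do not supply: six-month risks (the 20% draws partly on fiscal-year data), drop-out by arm, the share of occluders terminated, the visit interval, the hazard shape, and drop-out independent of occlusion. Only secondary outcomes are affected, so this is a change that should be made, not one on which the primary conclusion depends.

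**What to change.** Add to Statistical Analysis:

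> Time from randomisation to first partial or complete occlusion will be analysed in all randomised participants by assigned group, with Kaplan-Meier curves, a log-rank test and a Cox hazard ratio with 95% CI. Participants without occlusion are censored at 6 months or at their last port assessment, including those withdrawn when data collection stops. Withdrawal dates and reasons will be tabulated by group. Time between occlusions will be described among participants with repeat events, without a t-test between groups.

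The last sentence drops a between-group test because gap times exist only for participants with at least two occlusions, a subset selected by the outcome after randomisation.

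The sentence that ends participation at one of the listed risks must be reconciled with the secondary outcomes and termination rules that presuppose follow-up after a first occlusion. Exit dates for repeat events cannot be defined until then.

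Optional additions are restricted mean days patent to 6 months from the Kaplan-Meier curves, which keeps the days scale, and competing-event and interval-censored analyses.

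**Cost.** Plan wording and modest extra analysis, with no change to sample size or primary outcome. Visit dates and patency are already on the Record of Flushes. Withdrawal date and reason must be confirmed for each participant, before the enrollment log is destroyed after data cleaning. The log-rank test assumes non-informative censoring and has less power than a comparison of mean days if the excess is early.

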Setting for the Study: TCI Infusion Centers, specifically: the TCI Good Samaritan (GS) Infusion Center at GSH; the TCI GS Infusion Center Butler County; the the TCI GS Infusion Center at the Thomas Center; the TCI GS Infusion Center, Cheviot; the TCI GS Infusion Center, Medicenter; the TCI GS Infusion Center, Anderson; and the McCullough Hyde

Memorial Hospital infusion center. In January 2018, University of Cincinnati Medical Center Barrett Infusion Center was added as a data collection site.

Participants: Patients receiving care in the identified settings who have an implanted port catheter will be recruited to participate in this study.

Inclusion Criteria:

- over the age of 18 years
- able to read and understand English
- has an implanted port in place less than one (1) year
- evidence of a patent port catheter prior to enrollment in the study
- is receiving active treatment i.e., receiving a therapeutic drug through the implanted port
- current treatment protocol projected to continue for a minimum of three (3) months
- anticipates receiving care at the identified centers for 6 months following enrollment in the study
- receives routine care of the implanted port catheter at any of the identified data collection sites

Exclusion Criteria:

- has documented Heparin platelet antibody (could not be randomized to either group) or other allergy to Heparin
- receiving therapeutic dose of an anticoagulant, i.e., warfarin, heparin, enoxaparin, etc.
- has a heparin-coated port (for example BioFlo port)
- does not meet one or more of the inclusion criteria

Recruitment

Prospective study participants will be identified the day prior to their appointment in the treatment center by a member of the research team. Their chart will be reviewed for inclusion criteria and flagged as a potential study participant.

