 - HIT (Heparin induced thrombocytopenia as measured by a positive HIT antibody test)
 - Other heparin allergy

Moderating variables: other things that could also affect patency of the port

- Number of times port flushed per month or frequency of flushing.
- Use of prophylactic doses of anticoagulant drugs (e.g., enoxaparin, heparin, warfarin)
- Development of a hypercoaguable state, as diagnosed by primary hematologist/oncologist
- Mechanical difficulties related to port placement e.g. "Pinch-off syndrome"
- Length of time port has been in place prior to entrance in study

Extraneous variables:

- Type of cancer
- Age of participant

Data collection tool

The data collection tool (see Implanted Port Catheter Flushing Data Collection Form – Face Sheet: Appendix C and Record of Flushes: Appendix D) were developed by the principal and sub-investigators specifically for the purpose of this study. The tool was reviewed by the OPCC nurses for completeness and clarity. In addition to basic demographic information (age, gender), the nurse will record the patient's type of cancer, and the diagnosis or history of any hypercoaguable state or use of anticoagulant medication as documented in the patient chart. The nurse will also document the type of implanted port catheter (single/double), the port location (right/left, subclavian vein (described in the operative note or chest x-ray), and the date the port was inserted so that length of time the port has been in place can be calculated. Data will be recorded on the Face Sheet when the patient is enrolled in the study and as pertinent information/events become known, i.e., as complications occur.

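### The primary arm comparison is unadjusted although the protocol names and records baseline predictors of patency; a pre-specified adjusted risk difference would bring a modest gain in precision

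*Combined protocol and SAP*

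**What the plan says.** The Statistical Analysis section gives one rule for comparing the arms: "Differences between groups on the dependent variables will be calculated using t-test, Chi-Square" or Fisher's exact test, according to the level of data. It names no covariate or stratification factor. The sample size, under Recruitment, rests on an unadjusted two-group normal-approximation test of proportions.

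Two further analyses follow. The first is a regression: "Regression analysis will be used to determine the effect of the moderating variables on the occurrence of occlusion in the implanted ports". The second is a subdivision: "Participants in the control group and intervention group will be further stratified based on frequency of port flushing".

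The moderating variables, introduced as things that could affect patency, include prophylactic anticoagulant use and "Length of time port has been in place prior to entrance in study". Under Data collection tool, the Face Sheet takes anticoagulant use, single or double port, and "the date the port was inserted so that length of time the port has been in place can be calculated". Eligibility limits the range of that last variable: "has an implanted port in place less than one (1) year".

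Allocation is by sequentially numbered opaque sealed envelopes, and no stratification is described. Several infusion centers take part, and a second institution joined part-way: "In January 2018, University of Cincinnati Medical Center Barrett Infusion Center was added as a data collection site".

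**The concern.** The protocol identifies baseline factors that it expects to influence occlusion and collects them, but it leaves them out of the comparison that decides non-inferiority. The regression does not fill the gap, because its stated aim is the effect of the moderators. Nothing says that it includes arm, or that it yields a treatment difference on the scale of the margin. The one stratified comparison of arms uses flushing frequency, which is observed after randomisation and is not a suitable adjustment factor.

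Two things are at stake. Covariates that predict occlusion would narrow the confidence interval that is set against the 10-point margin. And since no stratified allocation is described, a chance imbalance in a predictive factor passes straight into the unadjusted difference.

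**Working it through.** **Inputs.** From the Recruitment section: control occlusion rate 20%, margin 0.10, one-sided alpha 0.05, power 80%, 198 per group. From the interim analysis text: final alpha 0.0471. Equal 20% rates in both arms under the alternative are an assumption; the plan's own figure confirms it.

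**Reproducing the plan.** n per arm = 2 × 0.20 × 0.80 × (z₀.₉₅ + z₀.₈₀)² / 0.10² = 0.32 × (1.645 + 0.842)² / 0.01 = 197.84 with unrounded quantiles, so 198. This matches.

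**Effect of adjustment.** Let R² be the share of outcome variance explained by baseline covariates. The documents give no covariate–outcome association, so R² is assumed and a range is shown.

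- SE = √[0.32 × (1 − R²) / 198]
- Power = Φ(0.10 / SE − z₁₋α)
- n per arm for 80% power at one-sided 0.05 = 197.84 × (1 − R²), rounded up

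| R² (assumed) | SE | Power, alpha 0.05 | Power, alpha 0.0471 | n per arm for 80% |
|---|---|---|---|---|
| 0 | 0.0402 | 80.0% | 79.2% | 198 |
| 0.01 | 0.0400 | 80.4% | 79.6% | 196 |
| 0.02 | 0.0398 | 80.7% | 79.9% | 194 |
| 0.05 | 0.0392 | 81.8% | 81.0% | 188 |
| 0.10 | 0.0381 | 83.6% | 82.9% | 179 |

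**What R² is plausible?** For a binary factor with prevalence q and risks p_hi and p_lo averaging 20%, R² = q(1 − q)(p_hi − p_lo)² / 0.16.

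- A 50/50 factor that doubles risk (13.3% versus 26.7%): 0.25 × 0.1333² / 0.16 = 0.028, giving power of 81.0% at alpha 0.05.
- R² = 0.10 from one 50/50 factor needs a difference of √(0.10 × 0.16 / 0.25) = 0.253, that is about 7% versus 33%, more than a fourfold risk. That row is an outer bound.
- Lumen type: the background section puts single-lumen ports above 95% of central lines in the TriHealth outpatient unit. Assuming 5% double-lumen with doubled risk (19.0% versus 38.1%), R² = 0.0475 × 0.1905² / 0.16 = 0.011.

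**Chance imbalance.** For the 50/50 factor that doubles risk, the SD of the between-arm difference in prevalence is √(2 × 0.25 / 198) = 0.0503. An imbalance of 1.96 SD is 9.9 points. It moves the risk difference by 0.0985 × 0.1333 = 0.013, or 1.3 points against a margin of 10.

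**The case against.** The strongest reply is that nothing is wrong. An unadjusted comparison of proportions is valid under randomisation, matches the basis of the sample size, and gives the stated power. That stands, and it limits the point to efficiency.

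The candidate covariates may also be weak. Time since insertion is capped at one year, therapeutic anticoagulation is excluded, and few ports are likely to be double-lumen. A realistic gain may be about one power point. That stands too.

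A reader might infer more than the documents support:

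- *That the plan ignores its baseline predictors.* It does not: a regression on the moderating variables is planned. The gap is that this regression is not the treatment comparison.
- *That treatment site is already recorded.* The visible text lists port location, which is anatomical, but not treatment site, among the Face Sheet items, moderating variables or extraneous variables. The form itself is not shown. Institution would be known operationally, since forms are held at each institution.
- *That adjustment is free.* The protocol is dated January 2020, and enrolment was under way by July 2019. Assignment is visible on stickers and colored sheets, alteplase use by group is assessed monthly, and two interim looks are planned. Changing the primary estimate at this stage needs a documented reason and a fixed covariate list.
- *That adjustment removes chance imbalance.* It deals only with the covariates in the model.

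The interim looks are a fair practical objection. At one third of 198 there are 66 per arm, and 132 × 0.20 is about 26 events, too few for a model with several terms.

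**Conclusion.** The point holds as a modest, optional improvement. The primary comparison leaves out baseline values that the protocol itself considers relevant and collects, and the planned regression does not supply an adjusted treatment difference against 0.10.

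For an assumed R² of 1% to 5%, the gain is 0.4 to 1.8 power points at one-sided 0.05 (80.4 − 80.0 and 81.8 − 80.0). At the final alpha of 0.0471, the same range gives 79.6% to 81.0% against 79.2% unadjusted, so a modest R² of a little over 2% would bring the final look back to 80%. There is also some protection against a shift of the order of 1 point from imbalance in a modelled factor.

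The size rests on the assumed R², on 20% occlusion in both arms, and on 198 analysed per arm. It would not support a claim that the planned test is invalid or that the trial is materially underpowered for want of adjustment. Adjustment also would not repair selection arising from withdrawals after randomisation.

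**What to change.** Amend the Statistical Analysis section as follows.

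- **Primary estimate at the final analysis:** the standardised (marginal) risk difference for first occlusion, from a logistic model with arm and a short pre-specified list of enrolment values. An odds ratio would not address an absolute margin.
- **Covariates:** port dwell time at entry; prophylactic anticoagulant use at enrolment; institution (TriHealth versus UCMC) if coded; lumen type only if numbers allow. Use the enrolment value of anticoagulant use, because the Face Sheet is also updated later.
- **Exclude from this model** moderators that can arise after randomisation: flush frequency, a new hypercoagulable state and mechanical difficulties. The separate moderator regression can keep them.
- **Decision rule:** compare the one-sided upper confidence limit, at the final alpha of 0.0471, with 0.10.
- **Unadjusted difference:** keep it as a sensitivity analysis at the end and as the analysis for the interim looks.

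The cost is small: some wording and code. Institution must be coded from study records, since it is not a listed Face Sheet item, and this should be done before the enrolment log is destroyed. The covariate list must be fixed and documented before outcome data are examined by arm. If interim or monthly by-group results have already been seen, the amendment should say so.

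### Stratifying and regressing on flush frequency observed after randomisation can create a false link between frequency and occlusion; use enrolment or pre-occlusion values

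*Combined protocol and SAP*

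**What the plan says.** - **Moderating variables.** The list includes "Number of times port flushed per month or frequency of flushing" and "Development of a hypercoaguable state, as diagnosed by primary hematologist/oncologist". It also names prophylactic anticoagulant use, mechanical difficulties, and how long the port was in place before entry. Only the last is fixed at baseline by its definition.
- **Data collection tool.** Dates and patency findings go on the Record of Flushes at every visit. The Face Sheet takes hypercoagulable history and anticoagulant use from the chart at enrolment, and is updated as events become known. Planned visit or flush frequency is not among the Face Sheet items described.
- **Experimental Aspect of the Study.** Visit frequency follows each participant's treatment plan and site policy. Occlusions are treated with alteplase, and occlusion at three visits in a row ends participation.
- **Statistical Analysis.** "Regression analysis will be used to determine the effect of the moderating variables on the occurrence of occlusion in the implanted ports". Then: "Participants in the control group and intervention group will be further stratified based on frequency of port flushing", with occlusion rates compared between the stratified groups. The text does not say whether this means arms within strata or strata against each other. The main comparison between arms uses unstratified tests.

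**The concern.** Flushes per month can be counted only as follow-up unfolds, and no rule stops the count at the first occlusion. If an occluded port is accessed more often because it occluded, or if follow-up is cut short by repeated occlusion, sorting by observed frequency sorts partly by outcome. The regression is exposed too, because its stated target is the effect of these moderators on occlusion, and reverse causation would corrupt that estimate. A hypercoagulable state that develops on study is likewise a post-randomisation finding, and nothing requires its diagnosis to precede the occlusion it is meant to explain.

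Two results are at stake: the reported relation between frequency and occlusion, and any comparison of saline with heparin within frequency strata, which randomisation would no longer protect.

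**Working it through.** **Step 1: the plan's own figure.** The power text (under Recruitment) gives the test ("using a two-group normal approximation test of proportions with a one-sided .05 significance level"), the size and power ("a sample size of 198 participants per group will have 80% power"), the control rate ("an approximate occlusion rate of 20% with the standard treatment") and the margin ("the difference in proportions between the proposed method and the standard method is greater than 0.10"). With 20% in both arms:

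n = (1.645 + 0.842)² × (0.2×0.8 + 0.2×0.8) / 0.10² = 197.8, so 198 per group.

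This reproduces, and it involves no stratification.

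**Step 2: an illustrative model.** These assumptions are not in the documents:
- half of each arm is planned low-frequency and half high-frequency;
- planned frequency has no effect, so both halves have the same risk p;
- a share q of planned-low participants who occlude is counted as high-frequency because of extra accesses.

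Then:
- low-stratum rate = p(1−q)/(1−pq)
- high-stratum rate = p(1+q)/(1+pq)

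**Step 3: false association between frequency and occlusion, p = 20% throughout.**

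| q | Low stratum | High stratum | Gap (true gap 0) |
|---|---|---|---|
| 0.10 | 0.18/0.98 = 18.4% | 0.22/1.02 = 21.6% | 3.2 points |
| 0.25 | 0.15/0.95 = 15.8% | 0.25/1.05 = 23.8% | 8.0 points |
| 0.50 | 0.10/0.90 = 11.1% | 0.30/1.10 = 27.3% | 16.2 points |

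**Step 4: saline minus heparin within strata.**

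| True rates, heparin / saline | q, heparin / saline | Low stratum | High stratum |
|---|---|---|---|
| 20% / 20% | equal, 0.10 to 0.50 | 0 | 0 |
| 20% / 30% | 0.10 / 0.10 | 9.5 points | 10.5 points |
| 20% / 30% | 0.25 / 0.25 | 8.5 points | 11.1 points |
| 20% / 30% | 0.50 / 0.50 | 6.5 points | 11.9 points |
| 20% / 20% | 0.10 / 0.25 | −2.6 points | +2.2 points |
| 20% / 20% | 0.25 / 0.50 | −4.7 points | +3.5 points |
| 20% / 30% | 0.25 / 0.50 | 1.9 points | 15.3 points |

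For example, at 20% vs 30% with q = 0.50 in both arms, the low stratum is 11.1% vs 0.15/0.85 = 17.6%, and the high stratum is 27.3% vs 0.45/1.15 = 39.1%.

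**Step 5: the odds scale.** The odds of occlusion are p(1−q)/(1−p) in the low stratum and p(1+q)/(1−p) in the high stratum. With equal q, the factor in q cancels between arms. At 20% vs 30% the odds ratio is (0.3/0.7)/(0.2/0.8) = 1.714 in both strata, which is the true value. The high-versus-low odds ratio does not cancel: it is (1+q)/(1−q), or 1.25/0.75 = 1.67 at q = 0.25, where the truth is 1.

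**Step 6: precision.** Two equal strata have 198/2 = 99 per arm. At 20% in both arms the 90% confidence interval half-width is 1.645 × √(0.32/99) = 0.094, and non-inferiority power within a stratum is about 55%.

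**The case against.** The mechanism is assumed. The protocol says occlusions are treated with alteplase; nowhere does it say that they bring extra visits or flushes, and it ties visits to the treatment plan. Flush dates are recorded, so frequency before the first occlusion could be computed, and the plan does not say that later flushes will be counted. All of this stands, and it limits the claim to what can happen. Equally, the plan does not exclude later flushes.

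A reader might infer that the stratified analysis will distort the saline-heparin difference. The documents do not support that. With equal true rates, as the sample size assumes, and equal reclassification, the difference within each stratum stays at zero. With equal reclassification the odds ratio is preserved even when the arms differ. Many of the shifts are also small beside a half-width of 9.4 points. Equal reclassification cannot be taken for granted, however: stickers and face sheets show the assignment, and alteplase may follow sluggish blood withdrawal, a bedside judgement.

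The regression is not described as estimating an adjusted saline-heparin effect, and no route from occlusion to a hypercoagulable state is shown. Both objections stand. They leave the false association between frequency and occlusion untouched, since it appears on both the risk and the odds scale even when the two solutions are equally effective.

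**Conclusion.** The concern holds as a possibility, confined to secondary analyses. As written, the outcome can feed into the stratifier and into the main regression covariate. The clearest consequence is a spurious association between frequency and occlusion of about 3 to 16 points for an assumed one tenth to one half reclassified. Within-stratum risk differences between arms are biased only if the arms truly differ or reclassification differs by arm; in the cases computed, the error runs from none to about 8 points. The reclassified share and the half-and-half split are assumptions, and the documents support no particular value.

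Two further inferences should be resisted. The trial's main conclusion is not at risk from this point, because the non-inferiority comparison is unstratified. Nor do the documents indicate that flushing intervals would be recommended from these strata: the research questions concern the flush solution and its complications. The point merits a change to the plan, but it does not undermine the design.

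**What to change.** In Statistical Analysis:

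1. Stratify by visit or flush frequency planned at enrolment, taken from the treatment plan, with cut-points set in advance. State whether arms are compared within strata or strata with each other.
2. Where planned frequency cannot be recovered, use only dated flushes before the first occlusion, already on the Record of Flushes. Use them either as a time-varying covariate or in a fixed early landmark window with occlusions counted afterwards. This is second best, because it is still measured after randomisation.
3. In the regression, include arm and only the enrolment values of the other moderators: port dwell time, prophylactic anticoagulant use and hypercoagulable history.
4. Report on-study frequency and diagnoses descriptively, and label the stratified results exploratory.

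The sample size does not change. The cost is some chart look-up, partly retrospective, because planned frequency is not a listed Face Sheet field. Plans may also change within the 6 months: eligibility requires treatment projected for only three, and one site has no policy on maintenance-flush frequency. The look-up must be done before the enrolment log linking study codes to medical record numbers is destroyed, which Privacy Information schedules for when data are entered and cleaned.
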